## **9.2. Radiation Therapy**

### **9.2.1 Immobilization and Simulation**

#### **9.2.1.1 Immobilization**

Patients will undergo radiation simulation in the supine position using the standard thermoplastic mask for immobilization to ensure daily reproducibility of treatments.

#### **9.2.1.2. Simulation Imaging**

Standard simulation CT guidelines from the vertex of the scalp through the tracheal carina, encompassing the entire head and neck.

### **9.2.2 Definition of Target Volumes and Margins**

GTV Gross Primary will include all existing gross disease at the primary site as seen on postoperative MRI and simulation CT scan. The CTV Primary Site will include the preoperative gross extent of primary tumor visible by imaging studies (CT, PET, and/or MRI), and/or clinical examination along with the postoperative surgical bed; for histologies with high risk of neutropic spread, a CTV Nerve will be created to encompass the affected nerve tracks. Fusion of preoperative and postoperative MRI to the simulation CT should be performed to aide in volume delineation. Irradiation of cervical and retropharyngeal nodal basins will be left up to the treating radiation oncologist. For patients in whom the cervical and retropharyngeal nodes will be treated, the CTV Node High Risk volume will include nodal basins wherein gross nodal was resected; CTV Node Low Risk will include nodal basins in which there was no gross nodal disease identified. If there are suspected grossly involved lymph nodes, a volume GTV Gross Node should be created. Skin bolus is acceptable and can be used for patients who are at high risk for skin involvement, at the discretion of the treating physician. Each CTV will be expanded by 3mm to a planning target volume (PTV), to account for intra-fractional patient motion, and inter-fractional setup error. The above are all standard radiation oncology treatment planning procedures.

### **9.2.3 Dose Prescription**

PTV Gross Primary = 70 Gy (relative biological effectiveness [RBE])

PTV Primary = 60 Gy (RBE)

PTV Nerve (if applicable) = 54 Gy (RBE)

PTV Gross Node (if applicable) =70 Gy (RBE)

PTV Node High Risk = 54 Gy (RBE)

PTV Node Low Risk = 51 Gy (RBE).

#### **9.2.4 Compliance Criteria and Dose-Volume Histogram (DVH) Analysis**

Standard of care target coverage will be applied. Target coverage for PBRT should achieve a D95  $\geq$  prescription dose and the PTV D05  $\leq$  110% of the prescription dose.

Organs at risk (OAR), including the parotid glands, submandibular glands, cochleas, oral cavity, larynx, esophagus, brachial plexus, brain stem, optic structures, and spinal cord, should be contoured according to standard guidelines for standard of care practice. A dose volume histogram will be constructed to evaluate target coverage and the doses to the surrounding OAR. The following standard of care radiation planning guidelines should be met:

- 1) Larynx:
  - a. <70 Gy (RBE) maximum point dose
  - b. <45 Gy (RBE) mean dose
- 2) Esophagus:
  - a. <34 Gy (RBE) mean dose to the esophagus
- 3) Brachial plexus:
  - a. <65 Gy (RBE) maximum point dose
- 4) Brainstem:
  - a. <54 Gy (RBE) maximum point dose
- 5) Optic nerves:
  - a. <54 Gy (RBE) maximum point dose
- 6) Optic chiasm
  - a. <54 Gy (RBE) maximum point dose
- 7) Spinal cord:
  - a. <45 Gy (RBE) maximum point dose to the spinal cord
- 8) Oral cavity:
  - a. <40 Gy (RBE) mean dose to the oral cavity excluding overlapping PTV
- 9) Contralateral parotid
  - a. <6 Gy (RBE) mean dose
- 10) Contralateral submandibular
  - a. <6 Gy (RBE) mean dose

#### **9.2.5 Treatment Planning Priorities and Instructions**

Critical normal structure constraints, specifically, the brain stem, spinal cord, optic structures will take priority over coverage of the tumor. This is followed by adherence to brachial plexus, larynx, esophagus, oral cavity, contralateral parotid, and contralateral submandibular glands.

#### **9.2.6 Planning**

The initial phase of 30 fractions will include all gross (PTV expansions of GTV) and microscopic (PTV expansions of CTV) disease volumes. The final boost of 5 fractions will include only gross disease (PTV expansions of GTV). Normally, this course of radiation treatment will take 7 weeks to complete.

Proton therapy will be planned in CMS XIO (Elekta; Stockholm, Sweden) and RayStation(Raysearch labs, Stockholm Sweden), and delivered with uniform scanning or pencil beam scanning. Physical and biological uncertainties will be evaluated and taken into account, and worst- and best-case scenarios with the ranges of uncertainty (2.5% \* range + 2mm) will be evaluated as per standard of care. We expect almost all patients to complete therapy.

### **9.2.7 Daily Treatment Localization**

Setup accuracy will be confirmed with daily x-ray orthogonal verification of the isocenter based on bony anatomy. Verification CT scans will be obtained at Procure or NYPC a simulation CT scan. This is all part of the standard of care and will be performed at least once in the course of treatment to assess for changes in anatomy and reproducibility, most often in the first and/or fourth week of treatment.

### **9.3 Cisplatin Chemotherapy**

Cisplatin should be administered on days 1-2, 21-22, and 42-43 of radiotherapy at a dose of 100mg/m2. The chemotherapy will be administered per MSKCC guidelines at 100 mg/m2 every three weeks. Normal scheduled treatment can be +/- 48 hours from three weeks post the prior administration. Administratoin entails pre-hydration with 1000 cc of Normal Saline (NS) and mannitol 25% before and after treatment. Fosaprepitant (150 mg), palonosetron (250 mcg), and decadron (12 mg) infusions are used for anti-emetic support before treatment. Cisplatin 100 mg/m2 is infused over one hour. Cisplatin can be administered before or after radiation is given but is only started once the radiation program has been initiated.

If the final surgical pathology report shows SNUC, at the discretion of the treating medical oncologist, the patient will receive an addition of etoposide chemotherapy to cisplatin chemotherapy. The dose of cisplatin will be decreased from 100 mg/m2 to 60 mg/m2. Cisplatin should be administered on days 1-2, 21-22 and 42-43 at a dose of 60 mg/m2 and Etoposide should be administered at days 1-3, 21-23, and 42-44 at a dose of 120 mg/m2. Infusion rate, anti-emetics, hydration will be administered as per institution's standard or physician's choice.

The post-chemotherapy administration protocol requires two days of intravenous hydration with 1000 cc NS following the day of cisplatin treatment in the chemotherapy suite. Dexamethasone 12 mg will be administered IV/PO on each of these days.

As needed anti-nausea medications will be prescribed for home and include Zofran 8 mg PO every 8 hours, Ativan 0.5 mg PO every 6 hours, and Compazine 10 mg every 6 hours. Patient will be advised to report any fever of 100.5 or greater or uncontrolled nausea or vomiting while at home.

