## **5.3 Cisplatin Chemotherapy**

Cisplatin should be administered on day 1 (+/- 3 days) of the start of radiotherapy and then every 3 weeks (unless there is a delay for safety concerns such as neutropenia) for a total of 3 cycles. Treatment can be given over 1 day or split over 2 days. The chemotherapy will be administered per MSKCC guidelines at 100 mg/m^2 (dose reductions after the first cycle allowed for toxicity). Normal scheduled treatment can be +/- 72 hours from three weeks post the prior administration. Administration entails fluid and anti-emetics as per institution standard. Cisplatin should be infused over one hour. Cisplatin can be administered before or after radiation is given but is only started once the radiation program has been initiated. If cisplatin treatment is contraindicated after the first cycle of treatment due to toxicity (e.g., kidney failure), a change in chemotherapy is allowed after a discussion with the medical oncology co-PI.

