## **5.4 Cisplatin with etoposide chemotherapy**

If the final pathology shows SNUC, at the discretion of the treating medical oncologist, the patient will receive cisplatin on day 1(+/- 3 days) of the start of radiotherapy and then every 3 weeks (unless there is a delay for safety concerns) for a total of three cycles. In addition to cisplatin at 60 mg/m^2 on day 1, the patient will receive etoposide chemotherapy at a dose of 120 mg/m^2 on days 1-3. Normal scheduled treatment can be +/- 72 hours from three weeks post the prior administration. The chemotherapy will be administered per MSKCC guidelines (dose reductions after the first cycle allowed for toxicity). Administration entails fluid and anti-emetics as per institution standard. Cisplatin can be administered before or after radiation is given but is only started once the radiation program has been initiated. If cisplatin treatment is contraindicated after the first cycle of treatment due to toxicity (e.g., kidney failure), a change in chemotherapy is allowed after a discussion with the medical oncology co-PI.

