### **11.5 Dose Modifications/ Delays**

At the discretion of the treating physician, any participant experiencing a grade 3 or higher toxicity may have a treatment break until resolution of the toxicity to grade 1 or less. If grade 3 toxicity persists, requiring a break of more than five consecutive treatments, the participant will be taken off protocol therapy per Section 13.0.

Cytopenias causing dose delays are not common with every three week dosing schedule and growth factors are not used in chemoradiotherapy protocols. Neutropenia of less than and ANC of 1000 and platelets of <100 would trigger a dose delay and re-assessment at 1 week. In the case of dose delays, the final dose of cisplatin may be given up to two weeks after completion of radiation therapy. Elevations in creatinine or BUN will be treated with extra sessions of intravenous hydration until the values normalize. Should the creatinine remain elevated between 1.4-1.6 mg/dl at the time of a subsequent dose, then cisplatin will either be dose reduced to 75 mg/m^2 or discontinued. The risks of permanent kidney damage with additional cisplatin will be discussed with the patient prior to further administration. For creatinine levels >1.6 further cisplatin will not be administered. Interruption of treatment may occur due to holidays, weather closing or machines are down.

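### Two different timing windows are written for the same 100 mg/m2 cisplatin regimen, and the only numeric cisplatin reduction level (75 mg/m2) lies above the 60 mg/m2 SNUC dose

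*Combined protocol and SAP*

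**What the plan says.** **Dosing window.** Sections 5.3 and 9.3 both describe cisplatin 100 mg/m2 every three weeks alongside proton radiation.

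- Section 5.3: "Normal scheduled treatment can be +/- 72 hours from three weeks post the prior administration".
- Section 9.3: "Normal scheduled treatment can be +/- 48 hours from three weeks post the prior administration".

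The two sentences differ only in the number of hours. Neither section refers to the other or states an order of precedence.

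**SNUC regimen.** If final surgical pathology shows SNUC, the medical oncologist may choose cisplatin with etoposide. Section 5.4 begins its dose statement "In addition to cisplatin at 60 mg/m" (squared), and Section 9.3 agrees on the amount: "Cisplatin should be administered on days 1-2, 21-22 and 42-43 at a dose of 60 mg/m2". Section 5.4 gives this regimen a 72-hour window. The SNUC paragraph of Section 9.3 gives no window of its own.

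**Renal rule.** Section 11.5 makes one statement for cisplatin as a whole: "Should the creatinine remain elevated between 1.4-1.6 mg/dl at the time of a subsequent dose, then cisplatin will either be dose reduced to 75" mg/m2, or stopped. Above 1.6 mg/dl no more cisplatin is given. The same section provides that "Elevations in creatinine or BUN will be treated with extra sessions of intravenous hydration until the values normalize". For the SNUC regimen, Section 5.4 also has "dose reductions after the first cycle allowed for toxicity", with no level stated, and "If cisplatin treatment is contraindicated after the first cycle of treatment due to toxicity (e.g., kidney failure), a change in chemotherapy is allowed" once the matter has been discussed with the medical oncology co-PI.

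**The concern.** Two sections that govern the same drug, dose, interval and patients should not allow different timing. Where they do, whether a dose was on schedule depends on which page staff or auditors open. For the main regimen, that makes the record of treatment delivery ambiguous.

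The renal rule matters for a different reason. Kidney failure is among the cisplatin side effects listed in Section 11.1.3, and 75 mg/m2 is the only numeric cisplatin reduction level in the documents. It fits a 100 mg/m2 start. SNUC patients have a written place in the trial (the end of the inclusion criteria, and Sections 5.4 and 9.3) with a lower start, and Section 11.5 neither excepts them nor says how its reduction branch applies to them.

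**Working it through.** The plan gives no figure to reproduce here. The check sets the sections side by side, with simple arithmetic.

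**Window, 100 mg/m2 regimen.** Three weeks = 21 days.

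| Section | Tolerance | Allowed interval from prior dose |
|---|---|---|
| 5.3 | 72 h = 3 days | 21 - 3 = 18 to 21 + 3 = 24 days |
| 9.3 | 48 h = 2 days | 21 - 2 = 19 to 21 + 2 = 23 days |

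- A dose within 48 hours of schedule satisfies both sections.
- The disputed zone is 72 - 48 = 24 hours on each side: more than 48 and up to 72 hours early or late.
- Three cycles give 3 - 1 = 2 intervals per patient. With the planned 25 patients, at most 25 x 2 = 50 intervals could be affected, and that only if all 25 receive three cycles of this regimen. The lower limit is 0. The documents give no basis for a figure in between.
- The fixed days in Section 9.3 add no conflict: from day 1 to day 21 is 20 days, and from day 21 to day 42 is 21 days. Both lie inside either window.

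**Renal level at creatinine 1.4-1.6 mg/dl.** The level is 75 mg/m2 (Section 11.5). The starting doses are 100 mg/m2 (Sections 5.3 and 9.3) and 60 mg/m2 (Sections 5.4 and 9.3).

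| Regimen | Start (mg/m2) | 75 minus start | Relative to start |
|---|---|---|---|
| Main | 100 | -25 | -25% |
| SNUC | 60 | +15 | 15/60 = +25% |

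For the main regimen, 75 mg/m2 is a reduction. For the SNUC regimen it is above the start, so that branch of the rule cannot do what it says.

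**What still works for SNUC.** Five routes do not depend on the 75 mg/m2 figure:

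1. The discontinuation branch at 1.4-1.6 mg/dl (Section 11.5).
2. The stop above 1.6 mg/dl, whatever the dose (Section 11.5).
3. Extra hydration (Section 11.5).
4. Reductions for toxicity with no stated level (Section 5.4).
5. A change of chemotherapy (Section 5.4).

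**The case against.** **On the window.** The wording is permissive and covers normally scheduled treatment. Delays for safety have their own routes in Sections 5.3 and 11.5, so the conflict mainly touches shifts of two to three days for other reasons. Following the narrower window satisfies both sections. The documents define no deviation category for dose timing, and no analysis in Section 14.0 uses it. All of this stands and limits the weight of the point. It does not remove the conflict, because no section says that 48 hours prevails and Section 5.3 expressly allows 72.

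**On the renal rule.** The rule has two branches, and discontinuation remains usable from a 60 mg/m2 start; the drafters may have meant just that for SNUC. The regimen is discretionary and may never be used. This too stands, but the text does not say that only one branch applies.

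**Stronger readings that the documents do not support.**

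- A reader might infer that SNUC patients have no renal rule, or that 75 mg/m2 is the only numeric renal step. The stop above 1.6 mg/dl is a second numeric step and applies to both regimens.
- A reader might infer that SNUC patients would probably have their dose raised. Section 11.5 speaks of a reduction, so a rise would contradict its own wording, and other routes are written.
- A reader might infer that Section 9.3 gives SNUC patients 60 mg/m2 on each of two days, against day 1 alone in Section 5.4. Section 9.3 uses the same two-day listing for 100 mg/m2 every three weeks, and describes the SNUC dose as lowered from 100 to 60. Two doses of 60 would make 2 x 60 = 120 mg/m2 per cycle, above 100. A cycle total is the supported reading, so this is not part of the point.

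**Conclusion.** Both inconsistencies hold on the current text, and both are minor.

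The window conflict is explicit for the 100 mg/m2 regimen only. It covers 24 hours on each side of the agreed range and between 0 and 50 dosing intervals, with no basis for a narrower estimate.

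The renal conflict is confined to one branch of a two-branch rule, where the stated level is 25% above the SNUC start. It reaches only patients whose final pathology shows SNUC, who receive cisplatin with etoposide, and whose creatinine remains at 1.4-1.6 mg/dl when a later dose is due. The planned mix of 15 squamous cell patients and 10 with other named histologies gives no expected number of SNUC patients, and it may be zero.

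The conclusion assumes that Sections 5.3, 5.4, 9.3 and 11.5 are all in force together, as nothing in the documents indicates otherwise. It does not touch the primary analysis or the decision rule of at least 17 of 25 patients alive, followed and free of local failure.

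**What to change.** The sponsor should reconcile two sets of sections:

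- Sections 5.3 and 9.3, on the dosing window for the 100 mg/m2 regimen.
- Sections 5.4, 9.3 and 11.5, on how the renal rule for creatinine 1.4-1.6 mg/dl applies to the 60 mg/m2 regimen.

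Which window, dose or renal rule is right is for the clinical team, and this review takes no view. The cost is amendment wording only; sample size, endpoint and analysis stay as they are.

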### **9.4 Permitted Supportive/ Ancillary Care and Concomitant Medications**

All supportive therapy for optimal medical care will be given during the study period at the discretion of the attending physician(s) within the parameters of the protocol, and documented on each site's source documents as ancillary care or concomitant medication.

### **9.5 Prohibited Therapies**

There are no explicitly prohibited therapies. Patients will be managed according to standard of care principles.

### **9.6 Duration of Therapy**

In the absence of treatment delays due to adverse event(s), treatment may continue as specified in the above treatment modality sections, or until one of the following criteria applies:

- Disease progression.
- Intercurrent illness that prevents further administration of treatment.

- Unacceptable adverse event(s).
- Patient decision to withdraw consent for participation in the study.
- General or specific changes in the patient's condition render the patient unacceptable for further treatment in the judgment of the investigator.

## 10.0 EVALUATION DURING TREATMENT/INTERVENTION

All patients will be evaluated according to the standard of care for their nasal cavity, paranasal sinus, skull base tumor.

### 10.1 Evaluation during concurrent chemo-proton radiotherapy treatment (please see Table 3 for details):

- Standard weekly treatment evaluations
- Weekly CTCAEv4 toxicity (Appendix 4) and adverse event assessment
- Clavien-Dindo Classification of Surgical Complications (Appendix 5)
- Patient completion of required patient reported outcome assessments including:
  - Study specific PRO instruments:
    - EORTC QLQ C30 & H&N 43
    - SBI

Table 3. ASSESSMENTS DURING PROTOCOL TREATMENT		
Assessments	Source	During Treatment
Toxicity and adverse events (CTCAEv4)	MD	Weekly throughout RT and at end of RT
Height and Weight	EMR	Postoperatively (pre RT), at week 4 of RT (+/- 7 days), and end of RT (+/- 7 days)
Postoperative MRI of the nasal cavity/paranasal sinuses	EMR	Should be completed 4 weeks post surgery (+/- 7 days)
History and Physical Exam	EMR	Safety evaluations during treatment with cisplatin involve weekly toxicity checks.
CBC and CMP	EMR	Safety evaluations during treatment with cisplatin involve weekly toxicity checks.
Clavien-Dindo Classification of Surgical Complication Assessment	MD	Postoperative but prior to radiation
EORTC QLQ C30 & H&N43	PSA	Postoperatively (pre RT), at week 4 of RT (+/- 7 days), and end of RT (+/- 7 days)
SBI	PSA	Postoperatively (pre RT), at week 4 of RT (+/- 7 days), and end of RT (+/- 7 days)

Abbreviations: MD (medical doctor); PSA (Patient self-administered with or without Research Study Assistant assistance); EMR (Electronic Medical Record)

### 10.2 Evaluation during follow up (please see Table 4):

- A focused history and physical exam
- Height and weight
- Dental evaluation
- Karnofsky performance status

- CTCAEv4 toxicity and adverse event assessment
- Study specific PRO instruments:
  - EORTC QLQ C30 & H&N43
  - SBI

Table 4. ASSESSMENTS IN PROTOCOL FOLLOW UP*					
Assessments	Source	From End of Treatment			
		3 months (+/- 2 weeks)	6 months (+/- 4 weeks)	12 months (+/- 4 weeks)	24 months (+/- 4 weeks)
History	EMR	X	X	X	X
Physical	EMR	X	X	X	X
Dental Evaluation	EMR		X	X	X
Karnofsky performance status	EMR	X	X	X	X
Toxicity and adverse events (CTCAEv4)	MD	X	X	X	X
MRI of nasal cavity/para-nasal sinuses AND PET/CT that includes diagnostic quality CT of neck.	EMR	X	x	X	X
EORTC QLQ C30/ H&N43	PSA	X	X	X	X
SBI	PSA	X	X	X	X

\*Additional follow-ups are allowed per standard of care but are not protocol mandated. The patient will not need to fill out these QOL questionnaires at regular cancer follow-up visits after the 24-month follow-up visit.

Abbreviations: MD (medical doctor); PSA (Patient self-administered with or without Research Study Assistant assistance); EMR (Electronic Medical Record)

## 11.0 TOXICITIES/SIDE EFFECTS

### 11.1.1 Expected side effects of endoscopic skull base surgery

The expected side effects of endoscopic skull base surgery are managed in a routine fashion in the outpatient setting. These include nasal crusting requiring in-office debridements, temporary decrease in smell and taste, foul smell and taste, and nasal congestion. Possible complications of endoscopic skull base surgery (with the rates as per the largest series) include carotid artery injury (<0.5%), non-life-threatening epistaxis (2%), postoperative CSF leak requiring conservative or operative intervention (5%). Corresponding rates among the endoscopic skull base surgery team here at MSKCC are 0%, 1.6%, 3.2%. We will use the Clavien-Dindo classification of surgical complications, which grades from I-V the morbidity related to a specific postoperative complication.

### 11.1.2 Expected side effects of radiation therapy

A list of the adverse events and potential risks associated with radiotherapy of the head and neck appear below and will determine whether dose delays and modifications will be made, or whether the event requires expedited reporting in addition to routine reporting.

Radiation side effects are typically divided into those that occur acutely (during radiation and up to 3 months after radiation), and those that occur later (>3 months post-radiation).

#### **11.1.3 Expected side effects of Cisplatin**

The side effects of cisplatin include, but are not limited to, nausea, vomiting, decreased white blood count (more susceptible to infections), decreased red blood cells (or anemia, with a risk of needing a blood transfusion), decreased platelets (making it easier to bleed), fatigue, reversible hair loss, electrolyte abnormalities (e.g., hyponatremia, hypokalemia, hypomagnesemia), hearing loss, neuropathy, and kidney failure.

